5.2.2.1 Adverse Events

Collected Variables:

- Event, i.e. diagnosis or signs/symptoms (text) [CRF – Cumulative adverse event form]
- The start and stop date of the event [CRF – Cumulative adverse event form]
- Outcome of event (categories: recovered/resolved, recovered/resolved with residual effects, recovering/resolving, not recovered/ not resolved, fatal, unknown) [CRF – Cumulative adverse event form]
- Severity (categories: mild, moderate, severe, life threatening or disabling) [CRF – Cumulative adverse event form]
- Treatment (categories: none, specific drug treatment, specific non drug treatment) [CRF – Cumulative adverse event form]
- Relationship with study device (categories: definitive, probable, possible, unlikely, none) [CRF – Cumulative adverse event form]
- Action taken with study device (categories: none, dose reduction temporarily, dose reduced, discontinued temporarily, discontinued) [CRF – Cumulative adverse event form]
- Pattern (categories: every study drug administration, intermittent, continuous, other) [CRF – Cumulative adverse event form]
- Seriousness (yes, no) [CRF – Cumulative adverse event form]

Derived Variables:

- Adverse Events (AEs): an adverse event is any untoward medical occurrence in a subject or clinical study subject administered a pharmaceutical product and which does not necessarily have a causal relationship with this treatment. An AE can therefore be any unfavourable and unintended sign, symptom, or disease temporarily associated with the use of a medicinal product, whether or not considered related to the medicinal product. The definition covers the entire study period, independent of whether IP was administered or not.
- Serious adverse event (SAEs): Any untoward medical occurrence or response to a medicinal product that at any dose: results in death, is life threatening, results in in-subject hospitalization or prolongation of existing hospitalization, results in a persistent or significant disability/incapacity, is a congenital anomaly/birth defect or, important AEs that are not immediately life-threatening or do not result in death or hospitalization but may jeopardize the subject or may require intervention to prevent one of the other outcomes listed.

	Form	Form No.	1M-DMST-011-01-A1
	Statistical Analysis Plan	Page	Page 25 of 69
		Effective Date	07/05/2018

In the analysis serious adverse events will be identified by the variables "Seriousness" (yes, no).

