- Related AEs: in the analysis related AEs will be defined as AEs for which the relationship with study device is assessed as "definitive" or "probable" or "possible"
- Severe AEs: in the analysis severe AEs will be defined as AEs for which the severity is assessed as "severe" or "life threatening"
- Subjects who prematurely terminated the Study Due to AE: in the analysis subjects who prematurely terminated the study due to AE are defined as those subjects with an adverse event for which the reason for early termination in the CRF end of study has been recorded as "adverse event"
- Death: death is defined as a fatal outcome of an AE.

Adverse events (AEs) will be reported on a per-subject basis. This implies that even if a subject reported the same event repeatedly, the event will be counted only once. In the latter case, the event will be assigned the worst severity and strongest relationship to the investigational study medication. The presentation of AEs is therefore restricted to the incidence per subject of AEs assigned to the Treatment Period.

Analysis Sets to be used for:	Tables	Safety analysis set
	Listings	Safety analysis set
	Figures	Not applicable

Adverse events will be summarized by default summary statistics by treatment group. Percentages will be calculated relative to the total number of subjects considered valid for the Safety analysis set.

Table 18. Summary of Adverse Events in the Single Dose Phase (Safety set)

Overview of AEs in the single dose phase including the:

- number of subjects with at least one AE.
- number of subjects with at least one device-related AE.
- number of subjects with at least one serious AE.
- number of subjects with at least one severe AE.
- number of subjects who prematurely terminated the study.
- Number of AEs
- Number of serious AEs
- Number of related AEs
- Number of severe AEs
- Number of deaths

Table 19. Summary of Adverse Events in the Multidose Phase (Safety set)

Overview of AEs in the multidose phase including the:

- number of subjects with at least one AE.
- number of subjects with at least one device-related AE.
- number of subjects with at least one serious AE.
- number of subjects with at least one severe AE.
- number of subjects who prematurely terminated the study.
- Number of AEs
- Number of serious AEs
- Number of related AEs
- Number of severe AEs
- Number of deaths

	Form	Form No.	1M-DMST-011-01-A1
	Statistical Analysis Plan	Page	Page 26 of 69
		Effective Date	07/05/2018

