Fatigue	n (%)	XX (XX.X%)	XX (XX.X%)	XX (XX.X%)

N: Number of subjects in specified treatment group

n: Number of subjects with data available

%: Percentage based on N

RUN: DDMMYYYY HH:MM <1MED > Page X of Y

Table 22. AEs by Relationship (Safety set)

	Statistic	Number of Subjects With at Least One AE in the single dose phase	Number of Subjects With at Least One AE in the multidose phase
TREATMENT A (N=XXX)			
Definitive	n (%)	XX (XX.X%)	XX (XX.X%)
Probable	n (%)	XX (XX.X%)	XX (XX.X%)
Possible	n (%)	XX (XX.X%)	XX (XX.X%)
Unlikely	n (%)	XX (XX.X%)	XX (XX.X%)
None	n (%)	XX (XX.X%)	XX (XX.X%)
TREATMENT B (N=XXX)			
Definitive	n (%)	XX (XX.X%)	XX (XX.X%)
Probable	n (%)	XX (XX.X%)	XX (XX.X%)
Possible	n (%)	XX (XX.X%)	XX (XX.X%)
Unlikely	n (%)	XX (XX.X%)	XX (XX.X%)
None	n (%)	XX (XX.X%)	XX (XX.X%)
TOTAL (N=XXX)			
Definitive	n (%)	XX (XX.X%)	XX (XX.X%)
Probable	n (%)	XX (XX.X%)	XX (XX.X%)
Possible	n (%)	XX (XX.X%)	XX (XX.X%)
Unlikely	n (%)	XX (XX.X%)	XX (XX.X%)
None	n (%)	XX (XX.X%)	XX (XX.X%)

N: Number of subjects in specified treatment group

n: Number of subjects with data available

%: Percentage based on N

Notes:

a) if a subject experienced more than one AE with the same event/diagnosis/sign/symptom, the AE with the strongest relationship will be counted.

RUN: DDMMYYYY HH:MM

<1MED >

Page X of Y

	Form	Form No.	1M-DMST-011-01-A1
	Statistical Analysis Plan	Page	Page 50 of 69
		Effective Date	07/05/2018

Table 23. AEs by Severity (Safety set)

Stat- istic	Treatment A (N=XXX)			Treatment B (N=XXX)			Total (N=XXX)		
	Mild	Moderate	Severe	Mild	Moderate	Severe	Mild	Moderate	Severe
Number of Subjects With at Least One AE In the single dose phase									
n (%)	X (X.X%)	X (X.X%)	X (X.X%)	X (X.X%)	X (X.X%)	X (X.X%)	X (X.X%)	X (XX.X%)	(X.X%)
Number of Subjects With at Least One AE In the multidose phase									
n (%)	X (X.X%)	X (X.X%)	X (X.X%)	X (X.X%)	X (X.X%)	X (X.X%)	X (X.X%)	X (XX.X%)	(X.X%)

N: Number of subjects in specified treatment group

n: Number of subjects with data available

%: Percentage based on N

Notes: If a subject experienced more than one AE with the same event/diagnosis/sign/symptom, the AE with the maximum severity will be counted.

RUN: DDMMYYYY HH:MM

<1MED >

Page X of Y

	Form	Form No.	1M-DMST-011-01-A1
	Statistical Analysis Plan	Page	Page 51 of 69
		Effective Date	07/05/2018

Table 24. Summary of Vital Signs (Safety set)

Characteristic	Statistic	Treatment A (N=XXX)	Treatment B (N=XXX)	Total (N=XXX)
Parameter (unit)				

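### Tables 22 and 23 count subjects but take the worst grade or strongest relationship only within one AE term, so cells below the top category match neither usual summary (minor)

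*SAP*

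**What the plan says.** In SAP 8.2.1.3, the Table 22 columns are headed "Number of Subjects With at Least One AE in the single dose phase" and "Number of Subjects With at Least One AE in the multidose phase". Its rows are the five relationship categories within each treatment group and in total. Table 23 uses the same unit as its row labels and splits it into Mild, Moderate and Severe. Neither shell has rows for AE terms. In both, the footnote on percentages is "Percentage based on N", where N is the size of the treatment group.

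The note to Table 22 says "if a subject experienced more than one AE with the same event/diagnosis/sign/symptom, the AE with the strongest relationship will be counted". The note to Table 23 says "If a subject experienced more than one AE with the same event/diagnosis/sign/symptom, the AE with the maximum severity will be counted".

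SAP 5.2.2.1 works at the same level. On repeated events it says "This implies that even if a subject reported the same event repeatedly, the event will be counted only once", and in that case "the event will be assigned the worst severity and strongest relationship to the investigational study medication". The grade is thus attached to the event, not to the subject. Nothing in the SAP says where to place a subject who has different events of different grade or relationship, or that the categories of these two tables may overlap.

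Under SAP 4.6.1, investigator terms are shown as recorded in the CRF and coded only on request. Protocol 12.9.1 had planned MedDRA coding and a summary by System Organ Class, preferred term and intensity.

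**The concern.** Keeping the worst grade within a term suits a table that has a row for each term, such as the one the protocol planned. The SAP shells have no term rows but keep a within-term rule. The heading promises subjects, and a reader will normally take such a table in one of two ways: each subject once at the worst grade, or each subject in every grade experienced. The notes deliver neither.

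Safety and tolerability are the secondary objectives, and these two tables are the only planned ones that show the full spread of severity and relationship by group. If the rule stands, two subjects with the same pair of grades can be tabulated differently because of how their events were named. The categories also need not reconcile with the row for subjects with at least one AE in Tables 18 and 19.

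**Working it through.** The plan gives no AE counts and no figure to reproduce. The check applies the stated rule to a constructed example.

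**Inputs.** Planned group size 12 (SAP 2.5). Subjects are counted, and percentages are based on the group N (shells of Tables 22 and 23). The worst grade is kept within the same event term (notes to the tables; SAP 5.2.2.1). Assumed for illustration: four of the 12 subjects have AEs in one phase.

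- S1: headache mild, headache severe
- S2: headache mild, nausea severe
- S3: headache mild, nausea mild
- S4: rash mild, nausea moderate, fatigue severe

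**Step 1: apply the note.** S1 has one term, so only Severe is kept. S2 keeps Mild and Severe. S3 keeps Mild under two terms. S4 keeps Mild, Moderate and Severe. S1 and S2 each had one mild and one severe AE, yet S1 has one entry and S2 has two.

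**Step 2: count in four ways.**

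| Counting rule | Mild | Moderate | Severe |
|---|---|---|---|
| Note, distinct subjects per category | 3 (25.0%) | 1 (8.3%) | 3 (25.0%) |
| Note, each retained AE counted | 4 (33.3%) | 1 (8.3%) | 3 (25.0%) |
| Worst grade per subject | 1 (8.3%) | 0 (0%) | 3 (25.0%) |
| Any AE of that grade | 4 (33.3%) | 1 (8.3%) | 3 (25.0%) |

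Percentages are count/12: 1/12 = 8.3%, 3/12 = 25.0%, 4/12 = 33.3%. The first two rows differ because the heading counts subjects while the note speaks of the AE that is counted. The first row follows the heading and is used below.

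**Step 3: general ordering.** A subject whose overall worst grade is X has at least one term whose worst grade is X. A subject with such a term has at least one AE of grade X. So, for any grade:

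subjects by worst grade ≤ count under the note ≤ subjects with any AE of that grade.

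Here Mild gives 1 ≤ 3 ≤ 4. For the top grade the outer two counts are equal, because any severe AE makes the subject's worst grade severe. The Severe cell is therefore the same under all three. The same argument covers Definitive in Table 22.

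**Step 4: dependence on wording.** If the second entry for S1 had been recorded under a different verbatim term, S1 would also enter Mild. That cell would go from 3 to 4 (25.0% to 33.3%) with no change in what the subject experienced.

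**Step 5: reconciliation.** Under the note the entries number 3 + 1 + 3 = 7 for four subjects with an AE. The three extra entries are one from S2 and two from S4. Under worst grade per subject they number 1 + 0 + 3 = 4, which equals the row for subjects with at least one AE.

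**The case against.** There is a fair case that little is at stake.

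- **Other tables.** It is tempting to say that Tables 22 and 23 are the only summaries of severity and causality by group. They are not. Tables 18 and 19 give, by group and phase, the subjects with at least one severe AE and with at least one related AE. Those rows do not depend on the within-term rule. Listing 18 shows every AE with its severity and relationship, so any count can be rebuilt.
- **A group looking more severe.** A reader might infer that varied terms make a group look worse. Step 3 rules this out for the top category: the additional entries fall in lower categories, from subjects already counted higher.
- **The fourth CRF grade.** The CRF item is "Severity (categories: mild, moderate, severe, life threatening or disabling", and Table 23 prints three columns, so it might seem that the worst grade has no place. SAP 5.2.2.1 already defines severe AEs for the analysis to include life-threatening ones. What remains is labelling: that definition leaves out the disabling part of the CRF category, and note c) of Tables 18 and 19, which includes it, is not repeated under Table 23.
- **Meaning of the cell.** It would be too strong to say that the counts have no meaning. A cell can be read as subjects with at least one event whose worst grade is X, and SAP 5.2.2.1 lends that some support. But the SAP never states this for the tables, and it is not a summary that readers expect under the heading used.
- **Overlap as a convention.** Table 8 carries a note that subjects may fall in more than one violation category, so overlap is accepted elsewhere in the SAP. A similar note here would disclose the overlap, but would not remove the unequal treatment of S1 and S2 or the dependence on wording.

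The first three points stand and limit the scope. The last two stand in part. None of them makes the rule fit the table.

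**Conclusion.** The counting rule in Tables 22 and 23 does not fit their stated unit. Overlap needs different terms with different grades or relationships; two different AEs of the same grade cause none when distinct subjects are counted. The plan does not state the multiple entry; it follows from applying the notes as written.

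The impact is minor. It is limited to the descriptive distribution below the top category in a study of 24 healthy subjects, and no test or decision rule uses these tables. Each additional entry moves one cell by 1/12 = 8.3 points with 12 per group. The actual effect is nil if no subject has such a pattern and cannot be sized further without AE counts. Adding the percentages across categories would give a larger figure, but the shells never sum the categories, so that is not a fair measure of the error.

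The statement that the top category is unaffected assumes that cells count distinct subjects, as the headings say.

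**What to change.** In SAP 5.2.2.1 and in the notes to Tables 22 and 23, state that each subject is counted once per phase: at the highest severity over all of that subject's AEs in the phase (Table 23), and at the strongest relationship over all of them (Table 22). With no missing grades or relationships, the categories then sum to the row for subjects with at least one AE in Tables 18 and 19, which gives a simple programming check. The result also no longer depends on whether two entries share a verbatim term.

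As a labelling point only, repeat note c) of Tables 18 and 19 under Table 23, and align the definition of severe AEs in SAP 5.2.2.1 with the full name of the fourth CRF category.

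The cost is SAP wording and a small change to two table programs. No new data are needed.

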8.2.2 Listings

Listing 1. Subjects Who Prematurely Terminated the Study Prior to Randomization

Total Set (Screening failures only)

Screening number	Date of Study Termination	Primary Reason of Premature Termination	Comment, if applicable
XXXXXXXXX 099-9999	DDMMYYYY 22SEP2007	XXXXXXXXXXXXXXXXXXXX Lost to follow-up	XXXXXXXXXXXXXXXXXXXX Subject did not come to Visit 1

etc.

continued on next page

RUN: DDMMYYYY HH:MM <1MED > Page X of Y

Listing 2. Randomized Subjects Who Prematurely Terminated the Study

All Randomized Subjects

Screening number	Treatment group	Study Termination (Last Contact):		Last study Medication administration:		Primary Reason of Premature Termination	Comment, if applicable	
		Last visit attended	Date	Treatment Day	Date			
XXXXXXXXX 099-9999	XXXXXXXXXXX Treatment A	XX V2	DDMMYYYY 22SEP2007	XX 20	DDMMYYYY 17SEP2007	XX 15	XXXXXXXXXXXX Adverse Event	XXXXXXXXXXXXXX

etc.

continued on next page

RUN: DDMMYYYY HH:MM

<1MED >

Page X of Y

	Form	Form No.	1M-DMST-011-01-A1
	Statistical Analysis Plan	Page	Page 57 of 69
		Effective Date	07/05/2018

Listing 3. Visit Dates and Informed Consent Dates

All Randomized Subjects

Screening number	Treatment group	Informed Consent Date	Visit X				
XXXXXXXXX 099-9999	XXXXXXXXXXXX Treatment A	DDMMYYYY 22SEP2007	DDMMYYYY 27SEP2007	DDMMYYYY 30OCT2007	DDMMYYYY 30NOV2007	DDMMYYYY 28DEC2007	DDMMYYYY 30JAN2008
etc.							

RUN: DDMMYYYY HH:MM

<1MED >

Page X of Y

Listing 4. Analysis Sets

All Randomized Subjects

Screening number	Treatment group	Safety Analysis Set	ITT Analysis Set	PP Analysis Set	Reasons for exclusion(s)
XXXXXXXXX 099-9999	XXXXXXXXXXXX Treatment A	XXX YES	XXX YES	XXX NO	XXXXXXXXXXXXXXXXXXXXXXXXXXXXXXXXXXXX SUBJECT HAD PROTOCOL DEVIATION
etc.					

RUN: DDMMYYYY HH:MM

<1MED >

Page X of Y

	Form	Form No.	1M-DMST-011-01-A1
	Statistical Analysis Plan	Page	Page 58 of 69
		Effective Date	07/05/2018

Listing 5. Demographics

Total Set

Screening number	Treatment group	Date of Assessment	Age (yrs)	Gender	Ethnic group	Height (cm)	Weight (kg)	BMI (kg/m^2)
XXXXXXXX	XXXXXXXXXX	DDMMYYYY	XX	XXXXXX	XXXXXXXXXX	XXX.X	XX	XX
099-9999	Treatment A	22SEP2007	30	MALE	CAUCASIAN	172.5	88	20
etc.								

RUN: DDMMYYYY HH:MM

<1MED >

Page X of Y

Listing 6. Minor and Major Protocol Violations

All Randomized Subjects

Screening number	Treatment group	Category of Protocol Violations	Details of Protocol Violations	Deviation Type
XXXXXXXX	XXXXXXXXXX	XXXXXXXXXXXXXXXXXXXX	XXXXXXXXXXXXXXXXXXXX	XXXXXXXXXX
099-9999	Treatment A	CONCOMITANT MEDICATIONS	INTAKE OF EXCLUSIONARY MEDICATIONS DURING THE STUDY	MAJOR
etc.				

continued on next page

RUN: DDMMYYYY HH:MM

<1MED >

Page X of Y

Form	Form No.	1M-DMST-011-01-A1
Statistical Analysis Plan	Page	Page 59 of 69
	Effective Date	07/05/2018

Listing 7. Treatment Compliance

Safety analysis set

Screening Number	Treatment Group	Visit	Was the investigational product delivered to the subject?	Was the investigational product taken correctly?
XXXXXXX	XXXXXXX	XXX	XXX	XXX
XXXXXXX	Treatment A	Visit 2	/	YES
etc.				

RUN: DDMMYYYY HH:MM

<1MED >

Page X of Y

Listing 8. Compliance to study procedures [1]

Safety analysis Set

Screening Number	Treatment Group	Visit	Was the subject fasting for at least 10h before IP intake	Was the device taken by subject	Was the blood sampling taken	Was the V1-V2 diary given to subject	Was the V1-V2 diary checked and retrieved	Was the V2-V5 diary given to subject
XXXXXXX	XXXXX	Visit X	XXX	XXX	XXX	XXX	XXX	XXX
XXXXXXX	Treatment A	Visit X	YES	YES	YES	YES	YES	YES
etc.								

RUN: DDMMYYYY HH:MM

<1MED >

Page X of Y

Listing 9. Compliance to study procedures [2]

Safety analysis Set

Screening Number	Treatment Group	Visit	Was the V2-V5 diary given back to subject	Was the V2-V5 diary checked	Was the investigational product retrieved from subject	Was the V2-V5 diary retrieved from subject
XXXXXXX	XXXXX	Visit X	XXX	XXX	XXX	XXX
XXXXXXX	Treatment A	Visit X	YES	YES	YES	YES

etc.

RUN: DDMMYYYY HH:MM

<1MED >

Page X of Y

Form	Form No.	1M-DMST-011-01-A1
Statistical Analysis Plan	Page	Page 60 of 69
	Effective Date	07/05/2018

Listing 10. Physical Examination

Safety analysis Set

Screening Number	Treatment Group	Visit	System	Findings	Abnormalities
XXXXXXX	XX	XXXXX	XXXXXXXXXX	XXXXXXX	XXXXXXX
XXXXXXX	A	Visit X	Eyes Ears-Nose-Throat	Abnormal	XXXXXXX

RUN: DDMMYYYY HH:MM <1MED > Page X of Y

Listing 11. Pregnancy

Safety analysis Set

Screening Number	Treatment Group	Pregnancy test	Pregnancy test results
XXXXXXX	XX	XXXXX	XXXXXX
XXXXXXX	A	Done	Positive

RUN: DDMMYYYY HH:MM <1MED > Page X of Y

Listing 12. Prior and Concomitant Medications

Safety analysis Set

Screening Number	Treatment Group	Status	Reported Drug Name	Dose	Unit	Frequency	Dosage form	Route of administration	Indication	Start	Stop	Ongoing
XXXXXXX 099-9999	XXXXX Treatment A	P C	XXXXX DRUG NAME	XXX 200	XXXX IU	XXXX BID	XXXX TAB	XXXX OS	XXXXXX HYPERTENSION	DDMMYYYY 22SEP2007	DDMMYYYY 22OCT2007	XXXX No

etc.

Notes: a) P - Prior medications, C - concomitant medications.

RUN: DDMMYYYY HH:MM <1MED > Page X of Y

	Form	Form No.	1M-DMST-011-01-A1
	Statistical Analysis Plan	Page	Page 61 of 69
		Effective Date	07/05/2018

Listing 13. Medical History

Total Set

Screening Number	Treatment Group	Disease category	Details	Start date	Stop date	Ongoing
XXXXXXXX 099-9999 etc.	XXXXXX Treatment A	XXXXXXXXXXXX hepatobiliary	XXXXXXXXXXXXXX ILATERAL	DDMMYYYY --JAN2005	DDMMYYYY --FEB2005	No

RUN: DDMMYYYY HH:MM

<1MED >

Page X of Y

Listing 14. Inclusion Criteria

Total Set

Screening Number	Eligibility
XXXXXXXX	XXX
099-9999 etc.	Yes

RUN: DDMMYYYY HH:MM

<1MED >

Page X of Y

	Form	Form No.	1M-DMST-011-01-A1
	Statistical Analysis Plan	Page	Page 62 of 69
		Effective Date	07/05/2018

Listing 15. Exclusion Criteria

Total Set

Screening Number	Eligibility
------------------	-------------

XXXXXXX	XXX
---------	-----

099-9999	YES
----------	-----

etc.

RUN: DDMMYYYY HH:MM

<1MED >

Page X of Y

Listing 16. Listing of Primary Efficacy Variable

ITT Analysis Set

Screening Number	Treatment Group	Visit	Plasma concentration of coenzyme Q10
------------------	-----------------	-------	--------------------------------------

XXXXXXX	XX	XXXX	XX
---------	----	------	----

099-9999	A	Visit 2	XX
----------	---	---------	----

...

RUN: DDMMYYYY HH:MM

<1MED >

Page X of Y

	Form	Form No.	1M-DMST-011-01-A1
	Statistical Analysis Plan	Page	Page 63 of 69
		Effective Date	07/05/2018

Listing 17. Listing of Pharmacokinetic parameters

ITT Analysis Set

Screening Number	Treatment Group	AUC_t	C_max	T_max	Clearance	Volume of distribution	T_1/2
XXXXXXXXXX 099-9999	XX A	XXXX XXXX	XXXX XXXX	XXXX XXXX	XXXX XXXX	XXXX XXXX	XXXX XXXX

Etc.

RUN: DDMMYYYY HH:MM

<1MED >

Page X of Y

Listing 18. Listing of AEs: General

Safety Analysis Set

Screening Number	Treatment Group	Gender/ Age/Ethnicity	Event	Outcome	Severity	Treatment	Relationship with study device	Action Taken	Pattern	Serious	Start date	End date
XXXXXXXXXX 099-9999	XX A	XX/XX/XXX F/52/ASIAN	XXXXXXXX FIBROMYOMA	XXX UNKNOWN	XXXX MODERATE	XXXX NONE	XXXX NONE	XXXX NONE	XXXX OTHER	XX NO	DDMMYYYY 23FEB2006	DDMMYYYY 25FEB2006

...

RUN: DDMMYYYY HH:MM

<1MED >

Page X of Y

Form	Form No.	1M-DMST-011-01-A1
Statistical Analysis Plan	Page	Page 64 of 69
	Effective Date	07/05/2018

Listing 19. Listing of Deaths

Safety analysis Set

Screening Number	Treatment Group	Gender/Age/ Ethnicity	Event	Date Started /Date Stopped /Treatment Days	Severity /Serious	Rela- tion- ship	Drug Event	Concomitant Therapy	Action Taken With Study Medication/ /Led to Study	Outcome Termina- tion
XXXXXXXXXX	XXXXXXXXXXXXXXXXXX	X/XX/XXXXXX/ XXXXXXXXXXXXXX	XXXXXXXXXXXXXXXXXX/ XXXXXXXXXXXXXX	DDMMYYYY/ DDMMYYYY/ XX/XX	XXXX/XX	XXXXXXXXXX	XXXXXXXXXX/	XXXXXXXXXX	XXXXXXXXXX/ XX	XXXXXXXXXX
099-9999	Treatment A	F/54/ HISPANIC	FIBROMYOMA RIGHT SIDE	23FEB2006/ ONGOING/ 25	MODERATE	UNRELATED	NA/NO		UNKNOWN/ YES	

Notes: a) Death is defined as a fatal outcome of an (S)AE.

RUN: DDMMYYYY HH:MM

<1MED >

Page X of Y

	Form	Form No.	1M-DMST-011-01-A1
	Statistical Analysis Plan	Page	Page 65 of 69
		Effective Date	07/05/2018

Listing 20. Listing of SAEs

Safety Analysis Set

Screening Number	Treatment Group	Gender/ Age/Ethnicity	Event	Outcome	Severity	Treatment	Relationship with study device	Action Taken	Pattern	Start date	End date
XXXXXXXXXX	XX	XX/XX/XXX	XXXXXXX	XXX	XXXX	XXXX	XXXX	XXXX	XXXX	DDMMYYYY	DDMMYYYY
099-9999	A	F/52/ASIAN	FIBROMYOMA	UNKNOWN	MODERATE	NONE	NONE	NONE	OTHER	23FEB2006	25FEB2006
...											

RUN: DDMMYYYY HH:MM

<1MED >

Page X of Y

Listing 21. Listing of AEs Leading to Study Termination

Safety Analysis Set

Screening Number	Treatment Group	Gender/ Age/Ethnicity	Event	Outcome	Severity	Treatment	Relationship with study device	Action Taken	Pattern	Serious	Start date	End date
XXXXXXXXXX	XX	XX/XX/XXX	XXXXXXX	XXX	XXXX	XXXX	XXXX	XXXX	XXXX	XX	DDMMYYYY	DDMMYYYY
099-9999	A	F/52/ASIAN	FIBROMYOMA	UNKNOWN	MODERATE	NONE	NONE	NONE	OTHER	NO	23FEB2006	25FEB2006
...												

RUN: DDMMYYYY HH:MM

<1MED >

Page X of Y

Form	Form No.	1M-DMST-011-01-A1
Statistical Analysis Plan	Page	Page 66 of 69
	Effective Date	07/05/2018

Listing 22. Vital Signs in the Multidose Phase

Safety analysis Set

Screening Number	Treatment Group	Assess-ment Date	Sitting Visit	Sitting SBP (mmHg)	Heart DBP (mmHg)	Respiratory Rate (beats/min)	Temperature (acts/min)	Temperature (kg)
XXXXXXXXXX	Treatment A	DDMMYYYY	Visit X	XXX	XXX	XXX	XXX	XXX
		DDMMYYYY	Visit X	XXX	XXX	XXX	XXX	XXX
		DDMMYYYY	Visit X	XXX	XXX	XXX	XXX	XXX
		DDMMYYYY	Visit X	XXX	XXX	XXX	XXX	XXX
		DDMMYYYY	Visit X	XXX	XXX	XXX	XXX	XXX
		DDMMYYYY	Visit X	XXX	XXX	XXX	XXX	XXX
Etc.								

RUN: DDMMYYYY HH:MM

<1MED >

Page X of Y

Listing 23. Vital Signs in the single dose phase

Safety analysis Set

Screening Number	Assess-ment Date	Sitting Visit	Sitting SBP (mmHg)	Heart DBP (mmHg)	Respiratory Rate (beats/min)	Temperature Rate (acts/min)	Temperature (kg)
XXXXXXXXXX	DDMMYYYY	Visit 1	XXX	XXX	XXX	XXX	XXX
XXXXXXXXXX	DDMMYYYY	Visit 1	XXX	XXX	XXX	XXX	XXX
Etc.							

RUN: DDMMYYYY HH:MM

<1MED >

Page X of Y

1MED Regulatory & Clinical Development	Form	Form No.	1M-DMST-011-01-A1
	Statistical Analysis Plan	Page	Page 67 of 69
		Effective Date	07/05/2018

Listing 24. Listing of Plasma Concentration of Q10 in the Single Dose Phase

ITT Analysis Set

Screening Number	Time Point	Plasma concentration of coenzyme Q10
XXXXXXXXXX	XXXX	XX
099-9999	Visit 1 - H1	XX
...		

RUN: DDMMYYYY HH:MM

<1MED >

Page X of Y

Listing 25. Listing of Pharmacokinetic parameters in the Single Dose Phase

ITT Analysis Set

Screening Number	AUC_t	C_max	T_max	Clearance	Volume of distribution	t_1/2
XXXXXXXXXX	XXXX	XXXX	XXXX	XXXX	XXXX	XXXX
099-9999	XXXX	XXXX	XXXX	XXXX	XXXX	XXXX
Etc.						

RUN: DDMMYYYY HH:MM

[figure not shown]
<1MED >

Page X of Y

	Form	Form No.	1M-DMST-011-01-A1
	Statistical Analysis Plan	Page	Page 68 of 69
		Effective Date	07/05/2018

[figure not shown]
